15.1 Adverse Events

An AE is defined as any untoward medical occurrence associated with the use of a drug in humans, whether or not the event is considered drug-related. An AE can therefore be any unfavorable and unintended sign (e.g., an abnormal laboratory finding), symptom, or disease occurring after informed consent form is signed and dated, without any judgment about causality. Any pre-existing medical condition that worsens after first administration of the study medication will also be considered a new AE. The AE reporting period starts from the time the subject signs and dates the informed consent and until 30 days after the subject's last study visit. All Aes will be coded using the MedDRA 21.1.

Treatment-emergent adverse events are defined as any event that occurs or worsens on or after the study treatment is initiated. Adverse events recorded in the eCRF which began prior to treatment will not be included in the summary tables but will be included in the AE data listings.

An overall summary will be presented that includes the number of TEAEs and the number and percentage of subjects who experienced at least one TEAE, by treatment group. This summary will also include breakdowns of TEAEs further categorized as ocular (study eye, fellow eye, and both eyes separately) or non-ocular, serious TEAEs, TEAEs by maximum severity, TEAEs by maximum relationship to study medication, TEAEs by maximum relationship to study procedure, TEAEs by maximum expectedness, number of serious TEAEs, number of subjects with any serious TEAEs, and with TEAEs leading to death.

Additional summaries of TEAEs will be provided showing the number and percentage of subjects who experienced at least one TEAE. These summaries will be presented by system organ class (SOC) and preferred term (PT). Non-ocular TEAEs will be summarized using discrete summary statistics and presented by treatment group at the subject level by SOC and PT. Ocular TEAEs will be similarly summarized at the subject level for study eyes, fellow eyes, and both eyes separately. If a subject reports the same PT multiple times within the same SOC, that PT will only be reported once within that SOC. As with the PT, if a subject reports multiple conditions within the same SOC, that SOC will only be reported once. In the summary, SOC will be listed in ascending alphabetical order; PTs will be listed in order of descending frequency for all subjects within each SOC.

Separate summaries will be provided for the following categories of Aes:

- Ocular TEAEs in the study eye, fellow eye, both eyes

- Non-ocular TEAEs
- Ocular TEAEs related/possibly related to study medication
- Non-Ocular TEAEs related/possibly related to study medication
- Ocular TEAEs related/possibly related to study procedure
- Non-Ocular TEAEs related/possibly related to study procedure
- Serious TEAEs
- Serious TEAEs related/possibly related to study medication

Severity of an AE is defined as a qualitative assessment of the degree of intensity of an AE as determined by the Investigator or reported to him/her by the subject. The assessment of severity is made irrespective of relationship to study medication or seriousness of the event and should be evaluated according to the following scale:

- *Mild*: Present and noticeable, but not distressing, and no disruption of normal daily activities.
- *Moderate*: Discomfort sufficient to possibly reduce or affect normal daily activity.
- *Severe*: Incapacitating, with inability to work or perform normal daily activity.

The relationship of each AE to the study medication should be determined by the Investigator using these explanations:

- *Not Related*: The event is clearly related to other factors such as subject's clinical condition, therapeutic interventions, concomitant disease, or therapy administered to the subject and does not follow a known response pattern to the product.
- *Unlikely Related*: The event is most probably caused by other etiologies such as participant's underlying condition, therapeutic intervention, or concomitant therapy, or the delay between administration and the onset of the AE is incompatible with a causal relationship. Therefore, there is not a reasonable possibility that the AE was caused by the study medication.
- *Possibly Related*: The event follows a reasonable, temporal sequence from the time of study medication administration and/or follows a known response pattern to the study medication, but could have been produced by other factors such as the subject's clinical state, therapeutic interventions, or concomitant therapy administered to the subject.
- *Related*: The event follows a reasonable, temporal sequence from the time of study medication administration and/or follows a known response pattern to the study medication and cannot be reasonably explained by other factors such as subject's clinical state, therapeutic interventions, or concomitant therapy administered to the subject, and either occurs immediately following study

medication administration, or improves on stopping the study medication, or reappears on repeat exposure, or there is a positive reaction at the application site.

Summaries of TEAEs by maximum severity and by maximum relationship will be presented for ocular Aes and non-ocular Aes separately. The number of subjects with any TEAEs (along with percentages) will be tabulated by SOC and PT within each SOC by treatment group. To count the number of subjects with any TEAEs, if a subject has multiple TEAEs coded to the same PT within the same SOC, the subject will be counted once under the maximum severity or relationship..

Individual subject listing will be provide for all AEs, the AEs leading to death, serious AEs, COVID-19 related AEs, and COVID-19 related serious AEs.

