Any intravitreal injection can be associated with the risk of endophthalmitis, ocular inflammation, increased intraocular pressure (IOP) and retinal detachments. While investigators and study staff will be instructed that aseptic technique must be used at all times when handling the implant and applicator components, when loading the applicator, and when dosing the subject, there is an inherent risk of infection including endophthalmitis. Similarly, as with other ocular surgeries, there is a risk of cataract development. Increased IOP is a risk due to both the addition of an implant into the vitreous cavity, and because the implant contains dexamethasone. Corticosteroids, including dexamethasone, have been associated with increased IOP and the development of posterior subcapsular cataracts.

AR-1105 is formulated as a solid, biodegradable, rectangular prism-shaped implant of dimensions of approximately [REDACTED]. The implant is designed to undergo slow erosion of the biodegradable matrix of different poly D, L- lactic-co-glycolic acid (PLGA) polymers to provide delivery of dexamethasone. Dexamethasone, like other corticosteroids, is a potent anti-inflammatory agent that works by suppressing multiple genes which encode pro-inflammatory cytokines, chemokines, adhesion molecules and enzymes and other proteins that are activated during the inflammatory process ([Barnes 2006](#), [OZURDEX PI](#)). Steroid molecules readily diffuse across cell membranes and bind to glucocorticoid receptors (GR) in the cytoplasm. Thus activated, steroids control

inflammation both directly, by suppressing transcription of pro-inflammatory genes thereby reducing the expression of inflammatory proteins, or indirectly (i.e. a non-genomic mechanism) by inhibiting the effects of other transcription factors that regulate expression of genes which encode proinflammatory proteins.

In pre-clinical studies, Aerie has evaluated multiple formulations containing various [REDACTED]

The duration of dexamethasone exposure in ocular tissues following intravitreal (IVT) injection in rabbits was evaluated for 2 different clinical formulations of AR-1105 implants and for OZURDEX implants. Both AR-1105 implant formulations, AR-1105-CF1 and AR-1105-CF2, were well-tolerated and there were no mortalities or significant adverse clinical observations in the study.

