4. STUDY POPULATION SELECTION

4.1 Study Population

4.2 Inclusion Criteria

Subjects MUST meet all of the following criteria at the screening and baseline visits to enter into the study:

1. At least 18 years of age
2. Vision-loss attributed to clinically detectable ME associated with either CRVO or BRVO. Subjects may be treatment-naïve, or if previously-treated with a steroid, must have demonstrated response to treatment.
3. Duration of ME (defined as the time since initial diagnosis of ME) ≥ 9 months in subjects with CRVO and ≥ 12 months in subjects with BRVO. If both eyes are eligible, the study eye will be the eye with worse VA
4. Best-corrected visual acuity (BCVA) as measured by the ETDRS methodology of between 25 and 70 letters (+1.2 and +0.3 logMAR units or 20/320 and 20/40 Snellen equivalent) in the study eye
5. Retinal thickness in the central subfield (as measured by SD-OCT) of >290 μm (females) and >305 μm (males) if using a Cirrus (Zeiss) instrument, or if a Spectralis (Heidelberg) instrument is used, thickness should be >305 μm (females) or >320 μm (males) in the study eye
6. Be able to understand and willing to provide written informed consent
7. Be willing and able to adhere to the instructions set forth in the study protocol

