4.3 Exclusion Criteria

Subjects meeting any of the following criteria during the screening or baseline evaluations will be excluded from entry into the study:

Ophthalmic:

1. Presence of a clinically significant epiretinal membrane, active retinal or optic disc neovascularization, active or history of choroidal neovascularization, presence of rubeosis iridis
2. History or presence of herpetic infection, toxoplasmosis, chorioretinopathy

3. Subjects with moderate non-proliferative diabetic retinopathy (as defined by the [International Clinical Diabetic Retinopathy Disease Severity Scale, 2002, in AAO PPP 2017](#)) or worse in either eye are excluded from participation
4. Any active infection
5. Aphakia, significant posterior capsule tear or iris trauma in the study eye
6. Anterior-chamber intraocular lens
7. Clinically significant media opacity
8. History of glaucoma or changes in the optic nerve head indicative of glaucomatous damage or visual field loss
9. Ocular hypertension in the study eye at qualification which is >23 mmHg without treatment or >21 mmHg if currently taking one IOP- lowering medication. Use of ≥ 2 IOP-lowering medications (fixed-dose combination therapies count as 2 medications) will exclude the subject
10. History of corticosteroid-induced IOP increase in either eye (defined as a documented increase of >10 mmHg following any previous initiation of steroid therapy, [Pleyer 2013](#))
11. Ocular condition in the study eye that, in the opinion of the investigator, would prevent a 15-letter improvement in visual acuity (e.g. severe macular ischemia).
12. Received an intraocular steroid injection or implant (e.g. via subconjunctival, or intravitreal routes of administration) within 6 months or any anti-VEGF treatment within 2 months prior to screening; Prior treatment with fluocinolone acetonide implant (e.g. RETISERT® or ILUVIEN®) or pan-retinal photocoagulation (PRP) would exclude the subject.
13. Intraocular surgery (including intraocular laser surgery), corneal refractive surgery or eyelid surgery within 3 months prior to Visit 1 or anticipated need for ocular surgery or ophthalmic laser treatment in the study eye during the study treatment period
14. Currently using topical corticosteroids in the vicinity of the eyes within the 1 month prior to Visit 1
15. Periocular depot of steroids placed within 6 months prior to Visit 2

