9.2 Determination of Sample Size

This study is not powered to detect a pre-stated efficacy signal, but rather will be used to inform the design and power for future studies. With a sample size of 20 evaluable subjects per treatment group, the study will have 95% confidence of ruling out AEs with true incidence rates of 13.9% or higher within each treatment group. That is, with 20 subjects in a treatment group, if an AE of a specific type is not observed, then with 95% confidence, the true incidence rate of that adverse event is less than 13.9%.

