4.1 Method of Assigning Subjects to Treatment Groups

Providing none of the subjects experience any clinically-meaningful ocular adverse reactions (possibly) related to treatment with AR-1105 during the initial phase, the study will continue into the randomized phase. During the randomized phase of the study, subjects will be assigned in a 1:1 ratio to either AR-1105-CF1 or AR-1105-CF2.

5. Sample Size and Power Considerations

This study is not powered to detect a pre-stated efficacy signal, but rather will be used to inform the design and power for future studies. With a sample size of 20 evaluable subjects per treatment group, the study will have 95% confidence of ruling out adverse events (AE) with true incidence rates of 13.9% or higher within each treatment group. That is, with 20 subjects in a treatment group, if an AE of a specific type is not observed, then with 95% confidence, the true incidence rate of that AE is less than 13.9%.

6. Data Preparation

All reported study data will be recorded on the electronic case report forms (eCRF) supplied by Statistic & Data Corporation (SDC). Only the Principal Investigator and authorized study staff according to the Delegation of Responsibilities log are entitled to make entries in the eCRF.

After data are entered into the clinical study database, electronic edit checks and data review will be performed. All data validation specifications and procedures are detailed in the Data Validation Manual as a separate document. When the database has been declared to be complete and accurate, the database will be locked. Any changes to the database after data have been locked can only be made with the approval of the Sponsor and Trial Runners in consultation with SDC.

The final analyses outlined in this document will be carried out after the following have occurred:

- All data management requirements are met according to SDC standard operating procedures, including data entry, performance of edit and validation checks, documentation and resolution of data queries, and database lock with written authorization provided by appropriate SDC and Sponsor personnel.
- Protocol deviations have been identified and status defined (major/minor deviations).
- Analysis populations have been determined.

7. Analysis Populations

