15.2 Intraocular Pressure

Intraocular pressure will be summarized at each visit, using continuous and discrete summary statistics, including change from baseline and the proportion of study eyes with an increase from baseline in IOP of 10 mmHg or more and the proportion of study eyes with IOP of 30 mmHg or more.

A subject listing of IOP will also be produced. Increase from baseline in IOP of 10 mmHg or more or IOP of 30 mmHg or more will be flagged in the listing.

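### Cataract is reported over all treated subjects although eyes with a posterior-chamber lens may enter and cannot develop it

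*SAP*

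**What the plan says.** - **Named risk.** Protocol 1 (Introduction) says that corticosteroids "have been associated with increased IOP and the development of posterior subcapsular cataracts". Safety and tolerability are the primary objective (Protocol 2.1), and Month 6 safety data feed the choice of formulation (Protocol 3.1).
- **Lens status at entry.** Protocol 4.3 excludes aphakia and significant posterior capsule tear in the study eye (criterion 5) and "Anterior-chamber intraocular lens" (criterion 6). Criterion 13 bars intraocular surgery only in the 3 months before Visit 1. No criterion mentions a posterior-chamber lens.
- **Denominator.** SAP 15 runs every safety analysis on the Safety population, which SAP 7.1 defines as everyone who received study medication. On adverse events, SAP 15.1 says: "Additional summaries of TEAEs will be provided showing the number and percentage of subjects who experienced at least one TEAE". These are broken down by system organ class, preferred term and treatment group, with study-eye, fellow-eye and both-eye summaries kept separate.
- **Lens findings.** SAP 15.2 (Slit-Lamp Biomicroscopy Examination) bases percentages on subjects with a response and adds shift tables from baseline. Neither this text nor the table list in SAP 20 has a phakic denominator or a split by lens status.
- **Precision statement.** SAP 5 sets a cut-off of 13.9%: "With a sample size of 20 evaluable subjects per treatment group, the study will have 95% confidence of ruling out adverse events (AE) with" rates at or above that level. Protocol 9.2 puts the zero-event case as "the true incidence rate of that adverse event is less than 13.9" per cent.

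**The concern.** A rate is easiest to read when everyone in its denominator could have had the event. A study eye with an artificial lens cannot develop cataract, so each such eye adds to the denominator and never to the numerator.

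Two readings are then at stake. First, the product hypothesis is a lower-dose implant with fewer steroid-related events (Protocol 3.2). A low cataract percentage could be taken as support when it partly reflects how many eyes had already had lens surgery. Second, with about 20 subjects per arm, the arms can differ in their number of phakic eyes by chance, and the cataract percentages will then differ even if the formulations carry the same risk. The precision statement is worded for any type of adverse event, so a reader may also apply 13.9% to cataract risk in susceptible eyes.

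**Working it through.** **Inputs from the documents:** 20 subjects per arm, 95% confidence, stated bound 13.9% (Protocol 9.2, SAP 5).

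**Assumed, because the documents give no figure:** 10 to 18 phakic study eyes per arm of 20, and an illustrative cataract risk of 20% in phakic eyes.

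**Step 1. Reproduce the stated figure.** If no event is seen in n subjects, the one-sided 95% upper bound is 1 − 0.05^(1/n). For n = 20 this is 1 − 0.8609 = 0.1391, or 13.9%. The plan's figure is correct for 20 subjects. (A two-sided exact interval would give 16.8% and the rule of three 15.0%, so the one-sided exact bound is the one used.)

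**Step 2. Put the number at risk in place of 20.** For m phakic eyes:
- zero-event bound = 1 − 0.05^(1/m). For m = 14: 1 − 0.8074 = 19.3%.
- chance of at least one cataract if the true phakic risk is 13.9% = 1 − (1 − 0.139)^m. For m = 14: 87.7%.
- expected all-subject rate = phakic risk × m/20. For m = 14 and a risk of 20%: 0.20 × 14/20 = 14%.

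| Phakic eyes of 20 | Zero-event 95% bound | Chance of ≥1 cataract at 13.9% phakic risk | All-subject rate if phakic risk is 20% |
|---|---|---|---|
| 20 | 13.9% | 95.0% | 20% |
| 18 | 15.3% | 93.2% | 18% |
| 16 | 17.1% | 90.9% | 16% |
| 14 | 19.3% | 87.7% | 14% |
| 12 | 22.1% | 83.4% | 12% |
| 10 | 25.9% | 77.6% | 10% |

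**Step 3. Chance imbalance between arms.** Treat the phakic counts in two arms of 20 as independent binomials, as under simple randomisation. The probability that they differ by 4 or more eyes is 0.27, 0.26 or 0.23 at an assumed phakic share of 50%, 60% or 70%. At a phakic risk of 20%, a gap of 4 eyes moves the expected count by 4 × 0.20 = 0.8 events, or 0.8/20 = 4 percentage points. For example, 14 against 10 phakic eyes gives 14% against 10% with identical formulations. The allocation details in Protocol 5.4 are redacted, so whether lens status was balanced by design cannot be judged.

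**Step 4. Which eyes are at risk.** SAP 15.1 counts events that occur or worsen after treatment. A phakic eye with some lens change at entry can therefore still have a cataract event, so eyes phakic at baseline are the right at-risk set.

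**The case against.** The strongest reply is that nothing in the plan is arithmetically wrong. A percentage of treated subjects is the incidence among treated subjects, and the 13.9% bound is exact for that quantity whatever the lens mix. This stands. The concern is the missing companion figure and how the bound will be read for cataract.

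It can also be said that the effect is small and recoverable. The imbalance example is worth less than one expected event, and no between-arm safety test is planned. Ocular history is tabulated by arm (SAP 11.1), lens findings and all adverse events are listed, and SAP 1 allows supplementary analyses. With about 45 subjects, phakic counts could probably be pieced together. That lowers the stakes but does not correct the planned rate, and those counts are nowhere tied to cataract events.

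A reader might go further and infer that the IOP rates are diluted too, because previously treated subjects must have responded ("Subjects may be treatment-naïve, or if previously-treated with a steroid, must have demonstrated response to treatment") and Protocol 4.3 excludes "History of corticosteroid-induced IOP increase in either eye". The documents do not support this:
- Every study eye can have a pressure rise, so "the proportion of study eyes with an increase from baseline in IOP of 10 mmHg or more" has a valid denominator.
- The exclusion covers any earlier steroid use, so a subject naïve to RVO treatment may also have been filtered by it.
- Only a documented rise above 10 mmHg excludes. Smaller or unmeasured rises pass.
- The required response concerns the disease and says nothing about pressure tolerance.
- Any effect of the mix of naïve and previously treated subjects is zero if both groups have the same risk.

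**Conclusion.** The point holds for cataract. Eyes that cannot have a named steroid risk may enter, and no at-risk denominator is planned. The all-subject cataract rate equals the phakic share times the rate in phakic eyes. At assumed shares of 50% to 90% it is therefore half to nine-tenths of the rate at risk, and the zero-event bound in eyes at risk is 25.9% to 15.3%. The direction is certain if any pseudophakic eye enrols. The size is unknown, because the documents give no lens-status mix.

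Two broader readings should be avoided. One is that the primary safety rates as a whole are diluted: event types for which every treated subject is at risk are unaffected, and fellow eyes, being tabulated separately, add no dilution. The other is that 13.9% is wrong: it is right for 20 treated subjects and misleads only when read as cataract risk in susceptible eyes. This is a reporting gap worth closing, not a reason to change the sample size or eligibility.

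**What to change.** 1. **SAP 15.1 and the table list in SAP 20:** add cataract events involving the study eye with study eyes phakic at baseline as denominator, by arm, beside the all-subject percentage.
2. **SAP 15.2 (Slit-Lamp Biomicroscopy Examination):** give the lens rows of the shift table for the same phakic-at-baseline eyes as well.
3. **SAP 10 or 11:** show baseline lens status of the study eye (phakic or pseudophakic) by arm.
4. **Protocol 9.2 and SAP 5:** add that 13.9% bounds incidence among 20 treated subjects and, read as risk in susceptible eyes, holds only when all 20 are at risk.

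Optionally, show the two IOP threshold proportions by prior corticosteroid treatment for RVO, as description only. Protocol 6.2 records prior RVO treatments, ongoing medication and medication stopped in the 30 days before screening. It does not record lifetime steroid exposure, so the split should be labelled accordingly.

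The cost is SAP and protocol wording and a few table rows. No new visits are needed, since ocular history is taken at screening and the lens is examined at every visit. The case report form is not shown, so it should be confirmed that lens status can be derived from it. The downside is smaller denominators and less favourable bounds.
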